5.3 Study Treatment

5.3.1 Treatments Administered

Subjects will be administered intradermally the SNS-301 doses of 2.0×10^{10} and 1.0×10^{11} particles per administration according to the 3+3 dose-escalation schema described herein and for the 3.0 x 10^{11} particles per administration dose additional patients will be enrolled until at least 6 patients can be evaluated even if no DLTs are observed at the dose. Planned treatment may continue of additional doses of SNS-301 administered every 21 days.

5.3.2 Identity of the Study Treatment

5.3.2.1 Study Treatment Details

The HAAH Nanoparticle Vaccine drug substance is a recombinant bacteriophage lambda construct that is engineered to display a fusion protein of phage gpD and a portion of the HAAH protein sequence. The HAAH-1 λ (SNS-301) construct contains 199 amino acids from the N-terminal region (amino acids 113 – 311) of the molecule.

The drug substance is characterized by testing that includes appearance, pH, and identity by dot blot using HAAH-specific monoclonal antibody, impurities (bioburden, endotoxin, host cell protein), determination of size distribution by particle analysis, quantitation by particle analysis, protein determination and potency by antigen enzyme-linked immunosorbent assay (ELISA).

5.3.2.2 Study Treatment Administration

The vaccine will be delivered intra-dermally by a single-use 3M[®] hollow microstructured transdermal system (hMTS) device.

5.3.2.3 Handling and Storage of Study Treatment

5.3.2.3.1 Packaging and labeling

The study treatment, SNS-301, will be packaged by the Sponsor, and supplied in an open-label basis.

The supplies will be labeled as follows:

• Sponsor's name and address

- Study number
- Content of the vial
- Dosing instructions
- Batch Number
- "Caution: New Drug--Limited by Federal (or United States) law to investigational use."

5.3.2.3.2 Storage

The study drug product is stored at 2 - 8 °C. Temperature excursions to ≤ 25 °C for less than 24 hours are acceptable.

5.3.2.4 Handling/Responsibilities

The study Treatment administrator must store and administer the study treatment according to the instructions provided by the Sponsor.

All study treatments shall be dispensed in accordance with the Investigator's prescription and it is the Investigator's responsibility to ensure that an accurate record of study treatment issued and returned is maintained.

Any quality issue noticed with the receipt or use of a study treatment (deficiency in condition, appearance, pertaining documentation, labeling, expiry date, etc.) should be promptly notified to the Sponsor, who will initiate a complaint procedure.

Under no circumstances will the Investigator supply study treatment to a third party, allow the study treatment to be used other than as directed by this Clinical Trial Protocol, or dispose of study treatment in any other manner.

5.3.2.5 Study Investigational Treatment Management and Disposal

All unused study treatments should be discarded at the investigational site and a destruction certificate obtained. The study treatment Administrator will submit the copy of Product Accountability Log to the Sponsor.

A potential defect in the quality of the study treatment may be subject to initiation by the Sponsor of a recall procedure. In this case, the Investigator will be responsible for promptly addressing any request made by the Sponsor, in order to recall study treatment and eliminate potential hazards.

5.3.3 Method of Assigning Patients to Study Groups

This is an open-label dose-escalation study; no randomization will occur.

All patients who sign the informed consent form (ICF) will be assigned a patient study number. Patient eligibility must be verified by the Investigator. If a patient fails to meet an eligibility criterion during the screening period, then the Investigator will complete a screening failure form in the e-CRF.

The study treatment will be administered only to patients included in this study following the procedures set out in this clinical study protocol. Details of the exact time of administration of medication (day/month/year, hour:minute) and the labeling on SNS-301 vials will also be documented in the e-CRF.

Patient withdrawn from the study retain the same patient number. New patients must always be allotted a new patient number.

5.3.4 Selection of Doses for the Study

This is an open-label study. Sequential cohorts will be enrolled in the order they present. In the dose-escalation cohorts, 3 or 6 patients will be treated with successively higher doses of SNS-301: 2.0×10^{10} , 1.0×10^{11} and 3.0×10^{11} particles every 21 days.

5.3.5 Selection and Timing of Dose for Each Patient

The MTD will be determined over the first 21-day interval following a single dose of SNS-301 in 3 dose cohorts. The MTD will be considered the dose level lower than that dose which produces \geq 2 DLT.

Dose-escalation will proceed when once all patients in a cohort (unless the MTD is observed) have completed a 21-day safety evaluation following the first dose of study treatment in the cohort. Multiple patients can be in screening phase simultaneously, but the first eligible patient able to be treated will be assigned the next treatment slot that is available for study.

More specifically, the first patient of each dose level will be enrolled and assessed for DLTs during cycle 1. Subsequent patients in a cohort can be enrolled after a 21-day review for tolerability by the Medical Monitor, Sponsor and Investigator(s) has been completed in the first patient.

After evaluation of the safety data of 3 patients in cycle 1 of the 2.0 x 10^{10} particles per administration dose, if none of the first 3 patients experiences a DLT, then dose-escalation to the next level (1.0 x 10^{11} particles per administration) can occur. When one patient shows a DLT, an additional 3 patients will be enrolled at the same dose level. If no more than 1 out of 6 patients experiences a DLT, patient enrollment to the next dose level can start.

Patients who withdraw from the study during cycle 1 (Day 1 - Day 22 pre-dose) for reasons other than safety or toxicity will be replaced.

Subsequent dose-escalation will be conducted in the same manner.

If the MTD is not achieved at the dose level of 3.0×10^{11} particles per administration, further dose-escalation will not be conducted. Additional patients will be enrolled at the highest dose level until at least 6 patients can be evaluated even if no DLTs are observed at the dose.

Although the dose-escalation process is guided by the safety evaluation during cycle 1, the global safety profile of SNS-301 at each dose level will be considered and discussed with the Investigator before increasing doses.

Planned treatment may continue for additional doses of SNS-301, administered every 21 days.

In patients who tolerate SNS-301, additional treatment may be continued with single doses of SNS-301 at their current dose level every 21 days, to maintain geometric mean titer (GMT) of HAAH antibodies to no less than 4 times the baseline value for at least six months (9 injections).

Treatment will be terminated with the 9th injection or will otherwise be terminated at any time upon the observance of PSA doubling < 90 days or occurrence of unacceptable toxicity. After termination, patients will be followed for an additional 6 months with monthly PSA levels and imaging studies as needed.

Once the MTD/RP2D is determined, patients receiving ongoing treatment may be escalated to that dose for subsequent treatments and receive a maximum of 9 injections. Patients who have received more than 9 injections due to the timing of the amendment limiting therapy to 6 months (9 doses), will be stopped at their last dose received and be followed for 6 months as with other patients. These subjects will continue to be followed for safety and biochemical PSA monitoring on a monthly basis for 6 months and are eligible to resume SNS-301 in case

of increases in PSA doubling to < 90 days or other evidence of disease progression and decline in immunological parameters.

5.3.5.1 Dose-limiting toxicities

Any of the following, if judged to be associated with SNS-301 (i.e., possibly-, probably-, or definitely related to), will be considered a DLT which are based on the NCI-CTCAE V4.03 criteria:

- 1) Grade 4 non-hematological toxicities (excluding alopecia) of any duration
- 2) Grade 3 non-hematologic (non-laboratory) toxicity lasting > 3 days despite optimal supportive care
- 3) Any Grade 3 or Grade 4 non-hematologic laboratory value if: a). Medical intervention is required to treat the subject; b), the abnormality leads to hospitalization; c). The abnormality persists for >1 week.
- Grade 4 hematologic toxicity, other than those specified in criteria 5 and 6 below, lasting > 7 days
- 5) Grade 3 or Grade 4 febrile neutropenia of any duration
- 6) Grade 3 thrombocytopenia in combination with a grade 3 or greater blood and lymphatic system disorder
- 7) Grade 3 AST or ALT that is associated with a grade 2 rise in bilirubin

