5.1 Overall Study Design and Plan Description

Figure 1: Dose-escalation study design (3+3 schema)

Following informed consent and screening, archived prostate tumor tissue and patient serum will be tested for the expression of HAAH. Patients who test positive for HAAH expression in either archived tumor tissue or fresh serum may be continued in the study. Baseline biochemical testing (chemistry, complete blood count [CBC], coagulation panel, CH50, and PSA) will be obtained prior to study treatment administration.

Treatment will consist of single repeated doses of SNS-301 administered every 21 days. A traditional 3+3 dose-escalation schema will be used to determine the MTD of SNS-301 for the first 2 doses and a modified dose-escalation schema with 6 patients per dose level for the remaining dose. Planned doses of SNS-301 are 2.0×10^{10} , 1.0×10^{11} and 3.0×10^{11} particles per administration diluted to 1 mL and administered intradermally. Additional patients will be enrolled at the highest dose level until at least 6 patients can be evaluated even if no DLTs are observed at the dose. Planned treatment may continue for two additional doses of SNS-301 administered every 21 days. Serum and whole blood samples will be obtained on the day of study treatment administration (Day 1) and 21 days thereafter. In patients who continue to receive study treatment, biochemical and immunologic testing will continue every 21 days.

The MTD will be determined over the first 21-day interval following a single dose of SNS-301 in 3 consecutive dose cohorts. The MTD will be considered the dose level lower than that dose which produces ≥ 2 DLTs in 3 or 6 patients. A DLT will be considered a protocolspecified drug-related grade 3-4 (National Cancer Institute Common Terminology Criteria for Adverse Events [NCI-CTCAE] V 4.03) adverse experience) (Section 5.4.5.1). The RP2D will be the highest dose administered if no MTD is observed.

Dose cohorts will be enrolled sequentially.

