5.3.5.2 Dose delay or reduction

In case of non-DLT AE (grade 2 NCI-CTCAE V4.03 drug related AE), the dosing interval of 3 weeks can be extended to up 42 days to allow the recovery from a related toxicity and the patient will resume at the same dose. If the patient experiences the same toxicity requiring a dose-delay at the subsequent cycle, the patient should be discontinued.

No sentinel safety assessment will be made; however, enrollment will be controlled so that a 21-day observation period is completed on the first subject in each cohort before any further enrollment is performed. Additionally, enrollment will be held if an ASR of grade 3 or greater is observed until the event resolves. In the event enrollment is held for an ASR, the Sponsor and PI will evaluate the outcome of the ASR and must agree to continued enrollment.

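### DLT criteria 6 and 7 name exact grades where minimum grades are evidently meant, so two narrow but worse events are not counted as DLTs while their milder forms are

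*Protocol*

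**What the plan says.** Protocol 5.3.5.1 gives seven DLT criteria, each applying only to events judged at least possibly related to SNS-301. The synopsis and SAP 6.3 repeat them. Those that matter here:

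- Criterion 1: non-hematologic Grade 4 toxicity of any duration.
- Criterion 3: Grade 3 or 4 non-hematologic laboratory values, subject to these conditions: "Medical intervention is required to treat the subject; b), the abnormality leads to hospitalization; c). The abnormality persists for >1 week".
- Criterion 4: "Grade 4 hematologic toxicity, other than those specified in criteria 5 and 6 below, lasting > 7 days".
- Criterion 5: "Grade 3 or Grade 4 febrile neutropenia of any duration".
- Criterion 6: "Grade 3 thrombocytopenia in combination with a grade 3 or greater blood and lymphatic system disorder".
- Criterion 7: "Grade 3 AST or ALT that is associated with a grade 2 rise in bilirubin".

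Criterion 2 is restricted to non-laboratory toxicity, so it cannot catch transaminase or bilirubin values.

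Protocol 5.3.5 applies the count. One DLT among three patients brings in three more, and then: "If no more than 1 out of 6 patients experiences a DLT, patient enrollment to the next dose level can start". Two or more DLTs at a dose put the MTD at the level below. Neither document says that the grades in criteria 6 and 7 are minimums. SAP 6.3 places derivation of the primary endpoints outside its scope, so it adds no clarifying rule.

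**The concern.** Where the authors want a range they write one: both grades are named in criteria 3 and 5, and criterion 6 gives a minimum for the partner disorder. Next to that, the bare grades for thrombocytopenia, AST/ALT and bilirubin read as exact grades. A patient whose platelets fall to Grade 4 instead of Grade 3, or whose bilirubin rises to Grade 3 instead of Grade 2, can then drop off the DLT list by getting worse.

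This looks like a drafting slip. Criterion 4 sets aside Grade 4 hematologic toxicities covered by criteria 5 and 6; for thrombocytopenia that makes sense only if criterion 6 was meant to reach Grade 4.

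The DLT count determines the primary endpoint. One uncounted event can turn 1/3 (expand) into 0/3 (escalate), or 2/6 (MTD exceeded) into 1/6 (dose acceptable).

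**Working it through.** **Step 1. Apply the criteria literally.** Criterion 1 is taken to include laboratory values, and conditions a, b and c of criterion 3 are taken as alternatives. These readings make the gaps narrowest.

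Thrombocytopenia with another blood or lymphatic disorder, not febrile neutropenia:

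| Platelets | Partner disorder | As written | With minimum grades |
|---|---|---|---|
| Grade 3, any duration | Grade 3 or 4, any duration | DLT (6) | DLT |
| Grade 4, ≤ 7 days | Grade 3, any duration | **not a DLT** | DLT |
| Grade 4, ≤ 7 days | Grade 4, ≤ 7 days | **not a DLT** | DLT |
| Grade 4, ≤ 7 days | Grade 4, > 7 days | DLT (4) | DLT |
| Grade 4, > 7 days | Grade 3 or 4, any duration | DLT (4) | DLT |

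If the partner is febrile neutropenia, criterion 5 counts the event whatever the platelet grade.

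Liver values resolving within 1 week, with no intervention and no hospitalization:

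| AST/ALT | Bilirubin | As written | With minimum grades |
|---|---|---|---|
| Grade 3 | Grade 2 | DLT (7) | DLT |
| Grade 3 | Grade 3 | **not a DLT** | DLT |
| Grade 3 | Grade 4 | DLT (1) | DLT |
| Grade 4 | Grade 2, 3 or 4 | DLT (1) | DLT |

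With intervention, hospitalization or more than 1 week, the Grade 3/Grade 3 case is a DLT through criterion 3.

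**Step 2. Look for text that closes the gaps.** Protocol 5.1 says "A DLT will be considered a protocolspecified drug-related grade 3-4" event, and SAP section 4 repeats this. It refers to protocol-specified events, so it points back to the list and adds nothing to it. Protocol 5.3.5.2 has "In case of non-DLT AE (grade 2 NCI-CTCAE V4.03 drug related AE", which suggests the authors saw non-DLT events as Grade 2 but does not make every Grade 3 or 4 event a DLT. Both support the view that minimums were intended; neither makes the two events count.

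**Step 3. Size.** The documents give no rate for these events. Let g be the assumed chance per patient of a gap event in cycle 1, p the DLT rate with the intended (minimum-grade) wording, and q = p − g the rate counted under the literal wording.

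- P(at least one gap event in n patients) = 1 − (1 − g)^n, with n = 12 (planned 3 + 3 + 6) or n = 18 (stated approximate total).
- P(escalate under 3+3) = (1 − q)³ + 3q(1 − q)⁵.
- P(at most 1 DLT in 6 at the top dose) = (1 − q)⁶ + 6q(1 − q)⁵.

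| g | 0 | 0.1% | 0.5% | 1% | 3% |
|---|---|---|---|---|---|
| Any gap event, n = 12 | – | 1.2% | 5.8% | 11.4% | 30.6% |
| Any gap event, n = 18 | – | 1.8% | 8.6% | 16.5% | 42.2% |
| P(escalate), p = 10% | 90.6% | 90.8% | 91.4% | 92.2% | 95.0% |
| P(escalate), p = 20% | 70.9% | 71.1% | 71.9% | 73.0% | 77.3% |
| P(escalate), p = 30% | 49.4% | 49.6% | 50.5% | 51.5% | 55.7% |
| P(≤ 1 of 6), p = 10% | 88.6% | 88.8% | 89.5% | 90.5% | 93.9% |
| P(≤ 1 of 6), p = 20% | 65.5% | 65.8% | 66.8% | 68.0% | 72.9% |
| P(≤ 1 of 6), p = 30% | 42.0% | 42.2% | 43.1% | 44.2% | 48.7% |

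Example: p = 20%, g = 1% gives q = 0.19, and 0.81³ + 3 × 0.19 × 0.81⁵ = 0.730, against 0.8³ + 3 × 0.2 × 0.8⁵ = 0.709 with the intended wording.

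**Step 4. Is escalation already over?** Protocol 3.4 allows for patients who had more than 9 injections when the amendment took effect. On a 21-day schedule the 10th injection falls on Day 9 × 21 + 1 = 190. Three cohorts, each with 21 days for the first patient and 21 for the rest, need at least 3 × 42 = 126 days. Escalation may therefore have finished, though slow enrollment or cohort expansion could have prolonged it.

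**The case against.** The gaps are real on paper but very small in practice. A patient also sampled at the lower grade while the partner abnormality is present meets criterion 6 or 7 as printed, so an event that worsens or recovers through that grade may still count. What remains is a short, drug-related, paired event in the first 21 days after one dose, seen only at the higher grade. Exclusion criterion 5 removes patients with low counts or raised liver values at screening, and Protocol 3.2 reports no effect on hematology or clinical chemistry in rats at doses up to the top planned level. Many investigators would read the grades as minimums. Escalation also requires 21-day reviews of the first and last patient in each cohort and a discussion of the global safety profile, and the synopsis lets the RP2D depart from the MTD on safety data. The 3% column is extreme: with an intended rate of 10%, it makes these events nearly a third of all DLTs. If escalation is over, an amendment changes no dosing decision.

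Most of this stands and limits the size of the problem, but it does not remove it. Scheduled cycle 1 laboratory draws are on Days 1, 8, 15 and 22 (Protocol Table 1), so a short event may be recorded at one grade only. The reviews rest on judgement and do not alter the DLT count. In a multi-center study the primary endpoint should not depend on each site correcting the text in the same way.

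**Conclusion.** The concern holds. Followed literally, criteria 6 and 7 give the wrong DLT count for two specific events, and nothing elsewhere in the protocol or SAP corrects it. The logical finding is certain on the narrowest reading of criteria 1 and 3; other readings would widen the gaps.

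The expected effect is small. For intended DLT rates of 10% to 30%, the probability of escalating rises by about 0.2 percentage points if g is 0.1% and by 4.4 to 6.4 points if g is 3%. The corresponding rise in P(at most 1 DLT in 6) at the top dose is 0.2 to 0.3 points and 5.3 to 7.3 points. These rates are assumptions, and the screening limits and rat data favour the low end. It is still worth correcting, because the definition decides the primary endpoint, the error lowers the count for a worse event, and the remedy is cheap.

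**What to change.** In the synopsis, Protocol 5.3.5.1 and SAP 6.3, add *or greater* after the thrombocytopenia grade in criterion 6, and after both the AST/ALT grade and the bilirubin grade in criterion 7.

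Then check the cycle 1 laboratory adverse events already recorded; Protocol 5.5.3.1 requires Grade 1 and above to be entered regardless of causality. If a gap event is found in a closed cohort, report the DLT count and the MTD/RP2D under both wordings. For any cohort still in cycle 1, count by the corrected wording. If escalation is over, this check is the most useful step, since it lets the sponsor state whether the MTD/RP2D depends on the wording.

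The cost is a short amendment, agreed and signed by all parties, with the IRB informed. Protocol 7.4 reserves amendments for exceptional cases, so it could be combined with another. A matching SAP edit is needed, and no new data are collected. The definition would change after some cycle 1 data exist, hence the dual reporting, and a few more events may count as DLTs.

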5.3.5.2 Dose delay or reduction

In case of non-DLT AE (grade 2 NCI-CTCAE V4.03 drug related AE), the dosing interval of 3 weeks can be extended to up 42 days to allow the recovery from a related toxicity and the patient will resume at the same dose. If the patient experiences the same toxicity requiring a dose-delay at the subsequent cycle, the patient should be discontinued.

No sentinel safety assessment will be made; however, enrollment will be controlled so that a 21-day observation period is completed on the first subject in each cohort before any further enrollment is performed. Additionally, enrollment will be held if an ASR of grade 3 or greater is observed until the event resolves. In the event enrollment is held for an ASR, the Sponsor and PI will evaluate the outcome of the ASR and must agree to continued enrollment.

5.4 Blinding

This was an open-label study, so there will be no blinding of study personnel.

5.4.1 Prior and Concomitant Treatment

All treatments being taken by the patients at entry to the study or at any time during the study in addition to the study treatment are regarded as concomitant treatments and must be documented in the appropriate screen of the e-CRF.

5.4.1.1 Allowed concomitant treatments

The following concomitant treatments are permitted during this study:

- Supportive treatment will be given as medically indicated.
- Prophylactic antiemetic premedication including corticosteroids and 5-hydroxytryptamine 3 antagonists.

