- a HAAH assessment: following informed consent, archived prostate tumor tissue and patient serum will be tested for the expression of HAAH. Only patients who test positive for HAAH expression in archived tumor tissue (if available) or fresh serum may be continued in the study. HAAH assessments are not subject to the 56-day screening window and are valid for 6 months. Patients who are negative for HAAH may be followed for 6 months and if PSA rises over that period time, they can enroll in the study provided that tissue or fresh serum is positive for HAAH
- b Biochemical testing (chemistry, complete blood count, coagulation, and total complement CH50,) to be obtained within 14 days prior to study drug administration if screening period is between 3 and 8 weeks. PSA levels are also to be evaluated at screening and within 14 days prior to study drug administration if screening period is between 3 and 8 weeks.
- c Immunologic blood collection: to be taken pre-dose on the day of study drug administration (Day 1) and every 21 days thereafter. Following the 9th dose (or last dose otherwise), PSA levels and other assessments will be followed on a monthly basis for 6 months. Patients with evidence of progression and declining HAAH immune parameters will have the option of resuming therapy on the study protocol.

- d Baseline radiological tumor burden evaluation consists of a baseline pelvic MRI or CT scan in addition to bone scan. These studies will need to be performed within 56 days (+ 7 days) prior to the start of the study.
- e Patients that have a delay in screening beyond 56-days may be re-screened for randomization.
- f Adverse events that occur post patient receiving study drug. Should Adverse event occur prior to patient receiving study drug they will be captured as Medical History.

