5.2.2 Exclusion Criteria

- 1. PSA doubling time of < 3 months
- 2. Participation in a clinical trial within 30 days prior to enrollment
- 3. Prior major surgery or radiation therapy within 4 weeks of enrollment
- 4. Any illness or condition that in the opinion of the Investigator may affect the safety of the patient or the evaluation of any study endpoint
- 5. Screening blood counts of the following: Hematopoietic:

Absolute neutrophil count $\leq 1500/\mu$ L,

```
Platelets \leq 100,000/\muL,
```

Hemoglobin \leq 9 g/dL;

Liver/Metabolic:

Alanine aminotransferase (ALT) and aspartate transaminase (AST) $\ge 2.5 \times ULN$ range, Total bilirubin $\ge 2 \times ULN$,

Albumin < 2.8 g/dL;

Renal:

Creatinine clearance \leq 50 mL/min as predicted by the Cockcroft-Gault formula

6. Subjects whose partners are WOCBP must use an adequate method of birth control while on study drug and at least for 3 weeks after discontinuation of study drug

- 7. Current or anticipated concomitant immunosuppressive therapy (excluding nonsystemic inhaled, topical skin and/or eye drop-containing corticosteroids)
- 8. Any concurrent condition requiring the continued use of systemic steroids (see above) or the use of immunosuppressive agents including methotrexate. All other systemic corticosteroids must be discontinued at least 4 weeks prior to first study treatment
- 9. Receipt of any blood product within 1 month of enrollment
- 10. Receipt of any vaccine within 4 weeks of enrollment
- 11. Active drug or alcohol use or dependence that, in the opinion of the Investigator, would interfere with adherence to study requirements
- 12. Been imprisoned or compulsorily detained (involuntarily incarcerated) for treatment of either a psychiatric or physical (i.e. infectious disease) illness
- 13. Patients who have a history of coagulopathies, thrombosis or who are receiving active anticoagulation for any condition, such as but not limited to, artificial heart valves, atrial fibrillation, etc.
- 14. Any other conditions judged by the Investigator that would limit the evaluation of a subject

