5.4.1.2 Prohibited Medications or Treatments During Study

Medications such as those listed below are not permitted in the course of the trial:

- Concurrent treatment with other investigational drugs
- Concurrent treatment with any other anticancer therapy including radiotherapy

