5.5.3.3 Administration site reaction

The area around the administration site will be assessed by the physician for adverse reactions at least 30 minutes post study drug administration. The Investigator will grade any ASRs according to the NCI-CTCAE V4.03 (excluding the actual expected micro-injection punctures).

Patients will be required to report any change in the administration site and return to the clinic for evaluation by the Investigator.

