6.1 Statistical and Analytical Plans

No formal statistical analysis will be performed, however, statistical derivation of all data will be derived by dose cohort and displayed for inspection.

For the dose-escalation phase of the study, cohorts of 3 or 6 patients will be screened, registered and treated at each dose level. The actual sample size may vary depending on the incidence of DLT during Cycle 1 at a given dose level. Once the MTD/RP2D is determined, additional patients may be accrued to provide for 6 patients in the MTD cohort. Approximately, 18 patients will be screened, registered and treated in the trial.

The primary safety analysis will assess MTD and AEs, clinical laboratory tests, and tolerability, based on the combined evaluation of immunogenicity and incidence of DLTs in each patient.

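### Protocol 5.4.1.1 allows corticosteroid premedication at vaccination without limits, although the entry criteria keep systemic steroids out of a trial that measures immune response (minor)

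*Protocol*

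**What the plan says.** Protocol Section 5.4.1.1 permits supportive care and, as a separate item, "Prophylactic antiemetic premedication including corticosteroids and 5-hydroxytryptamine 3 antagonists". It sets no route, dose, frequency or interval from vaccination.

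The entry criteria in Section 5.2.2 point the other way. Exclusion 7 covers "Current or anticipated concomitant immunosuppressive therapy (excluding nonsystemic inhaled, topical skin and/or eye drop-containing corticosteroids". Exclusion 8 bars conditions that need continued systemic steroids and adds: "All other systemic corticosteroids must be discontinued at least 4 weeks prior to first study treatment".

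Section 5.4.1.2 opens with "Medications such as those listed below are not permitted in the course of the trial" and then names only other investigational drugs and other anticancer therapy. Steroids and immunosuppressants are not mentioned.

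On the analysis side, SAP Section 8.4 tabulates concomitant medications, and Listing 16.2.4 shows them by patient. The Immunologic Population (SAP Section 5) and the immunological analysis (SAP Section 8.7) contain no rule for steroid exposure.

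**The concern.** The entry criteria treat systemic steroids as incompatible with a fair test of the vaccine. The on-study rules then allow them on the day of vaccination. If they are used, the response to vaccination could be blunted in cohorts of 3 to 6 patients with no control group, where a weak response at a dose level could not be told apart from a steroid effect.

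Several parts of the plan use the affected readouts:

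- Antibody titers, CTL responses and B- and T-cell responses are secondary endpoints (Protocol 4.2.2).
- The MTD becomes the RP2D by default, but pharmacodynamic data may override this (Synopsis, dose regimen). Section 5.1 counts antibody and T- and B-cell response as pharmacodynamic data.
- Section 6.1 describes the primary safety analysis as "based on the combined evaluation of immunogenicity and incidence of DLTs in each patient".
- A decline in immunological parameters is part of the basis for resuming treatment (Sections 5.1 and 5.3.5).
- A site reaction of grade 3 or more holds enrollment (Section 5.2.4). The post-dose check, "assessed by the physician for adverse reactions at least 30 minutes post study drug administration", falls when a premedication steroid could be acting.

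**Working it through.** The point is textual, and the plan gives no figure to reproduce.

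**Step 1. What the rules allow together.** Exclusion 7 exempts only non-systemic corticosteroids, so it treats systemic ones as immunosuppressive. Exclusion 8 requires 4 steroid-free weeks before the first dose. From the first dose onward the governing text is 5.4.1.1, which allows corticosteroid premedication expressly. The prohibited list is open-ended, but an implied ban cannot override an express permission. A systemic steroid at each dosing visit is therefore within protocol.

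**Step 2. When an effect could be seen.** Immunologic blood is "to be taken pre-dose on the day of study drug administration (Day 1) and every 21 days thereafter" (Table 1, footnote c). The first post-dose sample is at Day 22, so a steroid given on Day 1 matters only if the response is still lower about 21 days later. Sites are checked after dosing and again on Day 8, and patients must report changes and return for evaluation (5.5.3.3). Masking would therefore mainly concern the early check.

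**Step 3. Illustration of scale.** The following is assumed and comes from neither document: one patient's post-baseline titer is multiplied by r, baseline is unchanged, and the other patients are unaffected. In a cohort of n, the geometric mean is then multiplied by r^(1/n). Section 5.3.5 states the aim of continued dosing as "to maintain geometric mean titer (GMT) of HAAH antibodies to no less than 4 times the baseline value". Read as a cohort figure, the true fold rise needed to observe 4.0 is 4 / r^(1/n). Read for the exposed patient alone, it is 4 / r.

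| r | n = 3: multiplier; rise needed | n = 6: multiplier; rise needed | Exposed patient alone: rise needed |
|---|---|---|---|
| 0.75 | 0.909; 4.40 | 0.953; 4.20 | 4 / 0.75 = 5.33 |
| 0.50 | 0.794; 5.04 | 0.891; 4.49 | 4 / 0.50 = 8.00 |
| 0.25 | 0.630; 6.35 | 0.794; 5.04 | 4 / 0.25 = 16.00 |

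Across this range of r, the cohort geometric mean falls by 9% to 37% (n = 3) or 5% to 21% (n = 6). One exposed patient is 1/3 or 1/6 of a cohort; this is a scenario and not an estimate of use. The planned SAP figures show arithmetic mean and SD, and a log transformation is optional (SAP 8.7), so the reported summaries would not move by exactly these amounts.

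**The case against.** The strongest reply is that nothing is formally contradicted and nothing may have happened. Exclusions 7 and 8 govern entry, and 5.4.1.1 permits premedication without requiring or recommending it. Exposure may be nil. This stands, and it makes the clash one of purpose. It does not explain why the permission should remain. Since the pages between Sections 3.2 and 3.4 were not in the text I had, I draw nothing from the lack of a stated rationale.

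A second reply is that no stated rule turns on these readouts. This is partly right. Escalation and the MTD depend only on DLT counts. The fourfold titer is an aim of continued dosing; treatment stops at the ninth injection, a PSA doubling time under 90 days, or unacceptable toxicity. The combined evaluation in Section 6.1 has no operational criterion. But the RP2D can be changed on pharmacodynamic data, and resuming treatment refers to immune decline, so the readouts do have a use.

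A third reply is that exposure is traceable. That is correct. All treatments are recorded (Protocol 5.4.1), tabulated by ATC level 4 and listed, and SAP Section 7.4 allows labelled post-hoc analyses. In cohorts this small the listings can be read side by side. What is missing is a mark in the immune and site-reaction outputs themselves.

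Finally, steroids given to treat an adverse event would act on the same readouts. That also stands, so the mark should cover them too.

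**Conclusion.** The inconsistency is real and minor. The protocol expressly permits a class of drug on vaccination days that its own entry criteria treat as unacceptable, and no on-study rule or planned immune or site-reaction output deals with it.

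No size can be put on the consequence. The documents give neither the frequency of premedication nor its effect on titers, cellular responses or site reactions. The r^(1/n) figures only illustrate how far one patient can move a small cohort.

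A reader might infer more, and the documents do not support it:

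- That the MTD or dose escalation is biased through titers. No titer enters either rule.
- That a cohort missing a fourfold rise would be stopped or handled differently. The fourfold level is an aim attached to continued dosing of patients who tolerate the vaccine, with no consequence stated for missing it.
- That the immune results are already compromised. No use of steroid premedication is reported, and a titer effect would have to last about three weeks to reach the next draw.
- That steroid exposure would go unrecorded. It would be recorded and listed.

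The conclusion rests on reading 5.4.1.1 as including systemic corticosteroids, since it sets no limit on route, and on the premise behind exclusions 7 and 8 that systemic steroids can impair an immune response.

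**What to change.** **Protocol.** In 5.4.1.1, delete corticosteroids from the permitted premedication and keep 5-HT3 antagonists. In 5.4.1.2, add prophylactic systemic corticosteroids and immunosuppressants, except when given to treat an adverse event.

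**Doses already given.** From the recorded concomitant medications, identify every patient with any systemic steroid exposure during treatment. Mark these patients in the immune and site-reaction listings and outputs, showing prophylactic use and adverse-event use separately. Keep everyone in the main summaries. A summary without exposed patients is optional; with one exposed patient it would leave 2 of 3 or 5 of 6. If nobody was exposed, one sentence in the study report closes the matter.

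**Cost.** Two wording edits and a patient-level mark built from data already collected. Investigators lose one antiemetic option, while treatment of adverse events is unaffected. The protocol edit protects only the remaining doses, and Section 3.4 allows that some patients had already passed nine injections when the amendment took effect.
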